- Time to Hospital discharge (continuous): The time to Hospital discharge is defined as the time, in days, from the date of treatment start and the date of hospital discharge. In those patients who have not been discharged, the time, in days, from the date of first dose to the last available date will be calculated and it will be censored for time to event analyses. The description of the variable will be done separately depending on whether the patient has been discharged from hospital or not. The median and 95% confidence interval will be presented.
- Time from admission to Hospital discharge (continuous): The time to Hospital discharge is defined as the time, in days, from the date of admission and the date of hospital discharge
- Multivariate analysis will be done to evaluate the relationship of the main covariates in the analysis with Hospital discharge on Day 8 (Yes/No) and Hospital discharge on Day15 (Yes/No) by means of logistic regression models. More relevant exploratory covariates from the univariate analyses (p-value < 0.10) will be included in the multivariate analyses.
- Multivariate analysis will be done to evaluate the relationship of the main covariates in the analysis with time to hospital discharge by means of Cox proportional hazard models. More relevant exploratory covariates from the univariate analyses (p-value < 0.10) will be included in the multivariate analyses.
- Swimmer plot Hospital Discharge Day by Viral Load at Baseline, Disease Severity at Baseline and oxygen (yes/no) at baseline.

m) Class at discharge:

The time to hospital discharge (category 1) at 6-points ordinal scale will be analyzed by the Kaplan-Meier method and the median and the 95% confidence interval will be provided.

The analysis will be completed by the following subgroups:

- FDA classification
- Oxygen therapy on day 1
- Symptoms evolution less or equal/greater than 6 days.

The value of the 6-point ordinal scale will be derived from CRF data by using the following definition:

1. Discharge (Alive)
2. Hospital admission, not requiring supplemental oxygen.
3. Hospital admission, requiring supplemental oxygen.
4. Hospital admission, requiring high-flow nasal cannula or non-invasive mechanical ventilation.
5. Hospital admission, requiring extracorporeal membrane oxygenation or invasive mechanical ventilation.
6. Death.

In addition, the following analyses will be performed:

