APPENDIX III

12 EFFICACY EVALUATION

12.1 Efficacy evaluation

Table 12.1.1 Number of patients with PCR

Number of patients with PCR	Dose Cohort			
	1.5 mg N=X	2.0 mg N=X	2.5 mg N=X	Total N=X
Baseline				
Undetectable				
Positive				
Day ...				

Table 12.1.2 Viral load classification by dose level and total

Day	Viral Load at baseline (copies/mL)	Viral Load classification during treatment (copies/mL)			
		Low <4	Medium [4-7]	High >7	Total
Day 4	Low <4				
	Medium [4-7]				
	High >7				
	Total				
...(*)	Low <4				
	Medium [4-7]				
	High >7				
	Total				

(*) Days 7, 15 and 31

Listing 12.1.3 Viral load evolution

Subject id	Dose	Visit	Result	log10 viral load copies/mL

Table 12.1.4 Summary of Protocol-Specified Efficacy Endpoints. Cumulative results.

Endpoint from day 1 to	Dose Cohort			
	1.5 mg N=X	2.0 mg N=X	2.5 mg N=X	Total N=X
Patients discharged from hospital, n (%)				
Day 7				
Day 8				
Day 15				
Day 31				
Deaths at, n (%)				
Day 7				
Day 15				
Day 31				
Later than Day 31				
Patients requiring invasive mechanical ventilation and/or ICU admission at, n (%)				
Day 7				
Day 15				
Day 31				
Patients requiring invasive mechanical ventilation, n (%)				
Day 7				
Day 15				
Day 31				
Patients requiring ICU admission at, n (%)				
Day 7				
Day 15				
Day 31				
Patients requiring non-invasive mechanical ventilation at, n (%)				
Day 7				
Day 15				
Day 31				
Patients requiring oxygen therapy at, n (%)				
Day 7				
Day 15				
Day 31				
Patients requiring oxygen therapy (high flow) at, n (%)				
Day 7				
Day 15				
Day 31				
Patients requiring oxygen therapy (low flow) at, n (%)				
Day 7				
Day 15				
Day 31				

This table will be also performed by age (<65 vs. ≥65 year old (12.1.4.1)

This table will be also performed by FDA classification (12.1.4.2)

Table 12.1.5 Summary of Protocol-Specified Efficacy Endpoints. Non-cumulative results.

Endpoint	Dose Cohort			
	1.5 mg N=X	2.0 mg N=X	2.5 mg N=X	Total N=X
Patients discharged from hospital, n (%)				
Day 1 to Day 8				
Day 9 to Day 15				
Day 16 to Day 31				
Deaths at, n (%)				
Day 1 to Day 7				
Day 8 to Day 15				
Day 16 to Day 31				
Later than Day 31				
Patients requiring invasive mechanical ventilation and/or ICU admission at, n (%)				
Day 1 to Day 7				
Day 8 to Day 15				
Day 16 to Day 31				
Patients requiring invasive mechanical ventilation, n (%)				
Day 1 to Day 7				
Day 8 to Day 15				
Day 16 to Day 31				
Patients requiring ICU admission at, n (%)				

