	FDA risk groups at baseline			
	Mild	Moderate	Severe	p-value
Non-invasive mechanical ventilation, n (%)				
Yes				
No				
Invasive mechanical ventilation, n (%)				
Yes				
No				
High flow oxygen therapy, n (%)				
Yes				
No				
ICU admission, n (%)				
Yes				
No				
Days of hospital admission				
Days of symptom evolution				
CRP				
Ferritin				
AST				
ALT				
LDH				
Lymphocytes				

[figure not shown]
(*)It could be done by dose, if requested.

Figure 12.1.36 Plitidepsin: Viral load by Dose level (Median)

The lines represent the median value from baseline of the patients treated with viral load by central lab at the three dose levels in each time point(1.5mg n=x, 2.0 mg n=x, 2.5 mg n=x)

Figure 12.1.37 Plitidepsin: Viral load by Dose level (Mean)

The lines represent the mean value from baseline of the patients treated with viral load by central lab at the three dose levels in each time point (1.5mg n=x, 2.0 mg n=x, 2.5 mg n=x)

Figure 12.1.38 Plitidepsin: Viral load by FDA classification at baseline (Median)

[figure not shown]

Figure 12.1.39 Plitidepsin: Viral load by FDA classification at baseline (Mean)

[figure not shown]

Figure 12.1.40 Plitidepsin: Viral load by Oxygen support on day 1 (Median)

[figure not shown]

Figure 12.1.41 Plitidepsin: Viral load by Oxygen support on day 1 (Mean)

[figure not shown]
[figure not shown]
[figure not shown]

Figure 12.1.42 Time to negative detection of COVID-19 detection by PCR

[figure not shown]
(*) Table 12.1.37 will be also produced with median value and 95% confidence interval.

Figure 12.1.43 Time to Hospital discharge

[figure not shown]
(*) Table 12.1.38 will be also produced with median value and 95% confidence interval.

Figure 12.1.44 Time to Hospital discharge – All patients

[figure not shown]
(*) Table 12.1.39 will be also produced with median value and 95% confidence interval.

Figure 12.1.45 Time to Hospital discharge by FDA classification

(*) Table 12.1.40 will be also produced with median value and 95% confidence interval.

Figure 12.1.46 Time to Hospital discharge by time from symptoms (≤ 6 days vs >6 days)

(*) Table 12.1.41 will be also produced with median value and 95% confidence interval.

Figure 12.1.47 Swimmer Plot of Hospital Discharge Day by Viral Load at Baseline

[figure not shown]

Figure 12.1.48 Swimmer Plot of Hospital Discharge Day by Disease Severity at Baseline

[figure not shown]

Figure 12.1.49 Swimmer Plot of Oxygen therapy

[figure not shown]

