15.1 Overall Outcomes Discharge

Figure 15.1.1 Time to discharge per dose / FDA category

[figure not shown]
[figure not shown]

Figure 15.1.2 Probability of discharge per FDA category

FDA_class	6	7	8	9	10	11	12	13	14	15	16
Mild:	6	6	0	0	0	0	0	0	0	0	0
Moderate:	23	23	4	1	0	0	0	0	0	0	0
Severe:	16	15	8	7	5	3	2	1	1	1	1

Figure 15.1.3 Time to discharge per dose level (Moderate patients)

[figure not shown]
[figure not shown]

Figure 15.1.4 Duration of Hospitalization (Moderate patients)

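### Kaplan-Meier for time to discharge alive censors in-hospital deaths, so the curve overstates the probability of discharge once a discharge follows a death

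*SAP*

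**What the plan says.** SAP 8.1(l) defines time to hospital discharge from the start of treatment. For patients not discharged, the time from first dose "to the last available date will be calculated and it will be censored for time to event analyses". SAP 8.1(m) adds: "The time to hospital discharge (category 1) at 6-points ordinal scale will be analyzed by the Kaplan-Meier method". Category 1 of that scale is discharge alive and category 6 is death. Subgroup analyses are planned by FDA class, oxygen therapy on Day 1, and symptom duration up to or above 6 days.

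The output shells in SAP 12.1 are Figures 12.1.43 to 12.1.46, for example "Figure 12.1.45 Time to Hospital discharge by FDA classification". Each has a companion table among 12.1.38 to 12.1.41; for the first, "Table 12.1.38 will be also produced with median value and 95% confidence interval". No separate figure is listed for Day 1 oxygen. Appendix V (SAP 15.1) adds further discharge figures, including "Figure 15.1.1 Time to discharge per dose / FDA category" and "Figure 15.1.2 Probability of discharge per FDA category", and states no other censoring rule for them.

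Neither document names death as a competing event, specifies a cumulative incidence estimator, or gives dead patients a different censoring time.

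**The concern.** A patient who dies in hospital has not been discharged alive, so the rule censors that patient at or before the day of death. Kaplan-Meier assumes that a censored patient has the same future chance of discharge as those still in hospital. After death that chance is zero. The estimator in effect hands the dead patient's share of the curve to those discharged later.

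The curve can then contradict the SAP's own crude percentages for the same patients: Table 12.1.4 has a row "Patients discharged from hospital, n" (%), repeated by FDA class in Table 12.1.4.2. The distortion is largest in small groups with late discharges, such as the severe group or one dose arm. Dose selection draws on safety and efficacy data together (Protocol 6.1), so a curve by dose that conceals a difference in deaths would be unhelpful.

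**Working it through.** The SAP states no discharge probability, median or number of deaths for this analysis, so there is no planned figure to reproduce. The size has to be shown on assumed deaths.

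**Inputs.** The rows under Figure 15.1.2 (SAP 15.1) are read as numbers at risk on Days 6 to 16:
- Mild: 6, 6, 0
- Moderate: 23, 23, 4, 1, 0
- Severe: 16, 15, 8, 7, 5, 3, 2, 1, 1, 1, 1

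The first column sums to 6 + 23 + 16 = 45, the planned total, with 15 per arm (SAP 2.4). The rows do not separate discharges from deaths.

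**Assumptions.**
- 1, 2 or 3 of the 15 severe departures are deaths and all other departures are discharges.
- These patients remain in the analysed set.
- The one severe patient at risk on Day 16 is alive and censored.
- A departure is dated to the first day on which the patient is no longer counted. Another convention shifts the day labels, not the gaps.
- On the same day, discharges are counted before censored deaths (the usual Kaplan-Meier tie rule).

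**Formulas.** At a discharge time t with d discharges among n at risk:
- 1-KM rises by S_KM(t-) × d/n, where S_KM falls only at discharges.
- The Aalen-Johansen incidence rises by S_all(t-) × d/n, where S_all falls at discharges and deaths.

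The two are equal up to the first death. S_KM is larger afterwards, so 1-KM is too high from the next later discharge. A check on 5,000 random curves of 5 to 45 patients found no exception.

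**Severe group, one death.** The Day 16 incidence is 14/16 = 87.5% wherever the death falls.
- Death on Day 7: 15 remain, 14 are discharged, 1-KM = 1 - 1/15 = 93.3%. Gap 5.8 points.
- Death on Day 8: 1 - (15/16 × 9/15 × 1/8) = 93.0%. Gap 5.5 points.
- Death on Day 12: 1 - (3/16 × 1/2) = 90.6%. Gap 3.1 points.
- Death on Day 13, after the last discharge: 87.5%. No gap.

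**Severe group, more deaths (largest gap).**
- Two, on Days 7 and 8: 1 - (9/15 × 1/8) = 92.5% against 13/16 = 81.25%. Gap 11.3 points.
- Three, one on Day 7 and two on Day 8: 1 - (10/15 × 1/8) = 91.7% against 12/16 = 75.0%. Gap 16.7 points.

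**All 45, one death on Day 7.** 1 - 1/44 = 97.7% against 43/45 = 95.6%. Gap 2.2 points.

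**All placements.** There are 15 + 105 + 455 = 575 ways to place 1, 2 or 3 deaths among the 15 severe departures. For a 15-patient arm, every arm drawn from the 45 that contains exactly that many deaths was enumerated, because the documents do not split the rows by arm. The arm maximum is reached when 1-KM is 100%: 1/15, 2/15 or 3/15.

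| Curve | Deaths | Day 16 gap, points | Mean gap |
|---|---|---|---|
| Severe (16) | 1 | 0 to 5.8 | 4.7 |
| Severe (16) | 2 | 0 to 11.3 | 9.1 |
| Severe (16) | 3 | 0 to 16.7 | 13.2 |
| All 45 | 1 | 0 to 2.2 | 1.7 |
| All 45 | 2 | 0 to 4.2 | 3.4 |
| All 45 | 3 | 0 to 6.2 | 4.9 |
| One arm (15) | 1 | 0 to 6.7 | 4.8 |
| One arm (15) | 2 | 0 to 13.3 | 8.9 |
| One arm (15) | 3 | 0 to 20.0 | 12.1 |

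For the 23 moderate patients, with 1 or 2 of their own departures taken as deaths, the gap is 0 to 4.3 (1/23) or 0 to 8.7 (2/23) points.

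**Medians.** The median is unchanged in all 575 placements for the severe group and for all 45, and in every moderate placement. In a 15-patient arm it changes in 0.2%, 0.8% and 2.6% of compositions for 1, 2 and 3 deaths, mostly between Day 8 and Day 9.

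**Sensitivity to ties.** If deaths are counted before same-day discharges, the maxima become 5.8, 11.6 and 17.3 points (severe) and 2.2, 4.3 and 6.5 points (all 45). The severe median then changes in 49 of 575 placements, the all-45 median in none, and the arm figures become 1.0%, 3.7% and 10.0%.

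**The case against.** The strongest objection concerns the analysis set. The efficacy population (SAP 4.1) needs three doses and at least two weeks of follow-up, unless treatment was stopped because the disease worsened. Read literally, a patient who had all three doses and died on Days 7 to 13 is excluded rather than censored. Deaths after that open no gap on these rows, because no discharge follows them. This would reduce the number of censored deaths, but it would also remove failures from the denominator, which is no remedy. Figure 15.1.2 starts with all 45 at risk, so it shows no sign of exclusions. The point stands as a limit on the scenarios, which rest on the stated assumption that these patients are kept.

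Second, the tables report medians, and these hardly move. That is true; the effect lies in the later part of the plotted curves.

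Third, the number of deaths and the arm split are assumed. The sizes are therefore conditional, although the direction is not.

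Fourth, the censoring sentence does not mention death, and no estimator is named for Figures 15.1.1 and 15.1.3. Censoring of deaths nevertheless follows from a rule that covers everyone not discharged. For Appendix V the criticism applies only to curves drawn by Kaplan-Meier.

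Finally, the SAP counts death as failure elsewhere: in the good/poor outcome split of Appendix V, on the ordinal scale, and in the mortality tables. That limits the harm but leaves the discharge curve inconsistent with those outputs.

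**Conclusion.** The concern holds. As written, the rule censors in-hospital deaths in an analysis of discharge alive, and 1-KM is then too high from the first discharge that follows a death in the same curve. With 1 to 3 assumed deaths, the Day 16 overstatement can reach 5.8 to 16.7 points in the severe group, 6.7 to 20.0 points in one dose arm and 2.2 to 6.2 points overall. It is zero with no deaths, or with deaths only after the last discharge.

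The severity is minor. Time to discharge is not among the endpoints in Protocol 6.3, the curves are descriptive, the medians are nearly unaffected, and deaths are reported separately. Confidence is high in the mechanism and its direction. The size in this trial depends on deaths that the documents do not report.

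**What to change.** In SAP 8.1(l) and (m), state that in-hospital death is a competing event for discharge alive, that the cumulative incidence is estimated by Aalen-Johansen, and that only living patients are censored, at last contact. Apply this to Figures 12.1.43 to 12.1.46 with Tables 12.1.38 to 12.1.41, and to those of Figures 15.1.1 to 15.1.3 that are time-to-event curves. Keeping dead patients in the risk set to Day 31 is a simpler alternative that gives the same result, provided no living patient is censored earlier.

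The Cox model in 8.1(l) need not change for this reason: with deaths censored it estimates a cause-specific hazard.

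The cost is one or two sentences and a re-run. No new data are needed, because reasons for non-discharge (8.1(l)) and deaths (9.9) are already collected. If nobody died, the output is identical. If patients died before later discharges, the curves become somewhat less favourable.

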3 GENERAL PRINCIPLES

Planned analyses in this document will be carried out once the database is declared cleaned, closed and approved by Pharma Mar according to the premises described in the Data Management Plan version 2.0 approved on 09 June 2020.

Statistical analyses will be performed using SAS software version 9.4 and R. The results of the analyses will be presented in editable format (i.e rtf).

The data will be provided with one decimal place in general. In those cases where greater precision is required, as many decimal places as necessary will be provided.

Before to perform the analyses, the following activities will be performed:

Codification/revision and approval of the following terms:

- Adverse events /procedures according to MedDRA dictionary (latest version available).
- Medication according to the WhoDrug dictionary (latest version available).
- Reconciliation of serious adverse events in the study between the clinical database and the Pharmacovigilance database and resolution of all discrepancies.

Analysis will be done separately for each arm and the total population.

Continuous variables will be presented through the mean, median, standard deviation, range, Q1, Q3 and categorical variables will be presented through the distribution of frequencies and percentages; missing values will not be taken into account in the percentage calculation, percentages with valid data will be presented.

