Number of patients (%)	Dose Cohort							
	1.5 mg N=X		2.0 mg N=X		2.5 mg N=X		Total N=X	
	ICU admission*							
	Yes	No	Yes	No	Yes	No	Yes	No
Oxygen therapy at baseline								
Yes								
No								
Chronic Lung Disease								
Yes								
No								

(*) on day 7, 15 and 31.

Table 12.1.20 ICU admission

	Dose Cohort			
	1.5 mg N=X	2.0 mg N=X	2.5 mg N=X	Total N=X
Antiviral, n (%)				
Yes				
No				
Use of corticosteroids, n (%)				
Yes				
No				
Other COVID-19 treatment, n (%)				
Yes				
No				
High flow oxygen				
Yes				
No				
Invasive mechanical ventilation, n (%)				
Yes				
No				
Non-invasive mechanical ventilation, n (%)				
Yes				
No				

Table 12.1.21 ICU admission onset day and time to hospital discharge

Onset Day	Dose Cohort							
	1.5 mg N=X		2.0 mg N=X		2.5 mg N=X		Total N=X	
From first plitidepsin dose								
From onset of symptoms								
From ICU admission to hospital discharge								

Table 12.1.22 Hospital discharge

Endpoint	Dose Cohort							
	1.5 mg N=X		2.0 mg N=X		2.5 mg N=X		Total N=X	
Hospital discharge, n (%)								
Yes								
No								
Reason								

Table 12.1.23 Time to Hospital discharge

Days	Dose Cohort							
	1.5 mg Median (range)		2.0 mg Median (range)		2.5 mg Median (range)		Total Median (range)	
From first dose								
From admission								

Table 12.1.24 Multivariate analysis Hospital discharge on day 8

Variable	Value	DF	Estimate	Standard error	Wald Chi-Square	Pr > Chi-Square	Effect	Odds Ratio Estimate	Lower 95% Confidence Limit for Odds Ratio	Upper 95% Confidence Limit for Odds Ratio
..										

(*) Logistic regression.

Table 12.1.25 Multivariate analysis Hospital discharge on day 15

Variable	Value	DF	Estimate	Standard error	Wald Chi-Square	Pr > Chi-Square	Effect	Odds Ratio Estimate	Lower 95% Confidence Limit for Odds Ratio	Upper 95% Confidence Limit for Odds Ratio
..										

(*) Logistic regression.

Table 12.1.26 Multivariate analysis Time to hospital discharged

Parameter	DF	Parameter Estimate	Standard error	Chi-Square	Hazard Ratio	95% Lower Confidence Limit for Hazard Ratio	95% Upper Confidence Limit for Hazard Ratio	Pr > ChiSq
...								

(*) Cox regression.

Table 12.1.27 Invasive mechanical ventilation

Number of patients (%)	Dose Cohort							
	1.5 mg N=X		2.0 mg N=X		2.5 mg N=X		Total N=X	
	Invasive mechanical ventilation*							
	Yes	No	Yes	No	Yes	No	Yes	No
Oxygen therapy at baseline								
Yes								
No								
Chronic Lung Disease								
Yes								
No								

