15.3 Outcomes Inflammation Markers

Figure 15.3.1 Viral load evolution (mean) by FDA classification

[figure not shown]

Figure 15.3.2 Viral load evolution (mean) Moderate patients (FDA classification) by dose

[figure not shown]

Figure 15.3.3 Lymphocytes evolution (mean) by dose (Moderate patients)

[figure not shown]

Figure 15.3.4 C-reactive protein evolution (mean) by FDA classification

Figure 15.3.5 Neutrophils/Lymphocytes evolution (mean) by FDA classification

Figure 15.3.6 D-dimer (mean) by FDA classification

[figure not shown]

Figure 15.3.7 C-reactive protein evolution (mean) by dose (Moderate patients)
 Figure 15.3.8 Neutrophils/Lymphocytes evolution (mean) by dose (Moderate patients)
 Figure 15.3.9 D-dimer (mean) by dose (Moderate patients)

[figure not shown]

Figure 15.3.10 Inpatient time-variation of Neutrophil/Lymphocyte ratio (NLR), per dose cohort, and median trends

[figure not shown]

Figure 15.3.11 Inpatient C-Reactive protein time variation, per dose cohort, and median trends

[figure not shown]

Figure 15.3.12 Intra-patient time-variation in ALT (normalized values), per dose cohort, and median trends (ULN: Upper Limit of Normality)

[figure not shown]
[figure not shown]

Figure 15.3.13 Intra-patient time-variation in lymphocyte count, per dose cohort, and median trends.

15.4 Regression Model.

[figure not shown]
Figure 15.4.1 Logistic regression model – Discharge at D8

variable	OR	Regression Estimate	p-value
Baseline viral load	11.482	2.4408	0.0224
Dose: 2 mg/d vs 1.5 mg/d	0.268	-1.3169	0.4165
Dose: 2.5 mg/d vs 1.5 mg/d	0.0233	-3.7592	0.0561
FDA Moderate vs Mild	0.0687	-2.6784	0.2528
FDA Severe vs Mild	0.7775	-0.2517	0.9151
Age (continuous)	1.238	0.2135	0.0526

0.011 0.0620.250 1.00

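### All six FDA-Mild patients share one outcome at Day 8, so the planned logistic model has no finite odds ratio against Mild, and the FDA and dose rows of SAP Figure 15.4.1 cannot be reconciled with the SAP's own counts

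*SAP*

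**What the plan says.** SAP 8.1 l) plans multivariable models for "Hospital discharge on Day 8 (Yes/No) and Hospital discharge on Day15 (Yes/No) by means of logistic regression models". Covariates are chosen by a univariate screen: "More relevant exploratory covariates from the univariate analyses (p-value < 0.10) will be included in the multivariate analyses". The univariate test is not named.

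The shell "Table 12.1.24 Multivariate analysis Hospital discharge on day 8" has one row per parameter, with estimate, standard error, "Wald Chi-Square", odds ratio and 95% limits. Its footnote says only that this is logistic regression. Table 12.1.25 repeats the layout for Day 15. No penalised, exact or likelihood-ratio method is named. On software, section 3 says: "Statistical analyses will be performed using SAS software version 9.4 and R".

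Appendix V then shows two displays that bear on this model:

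- "Figure 15.1.2 Probability of discharge per FDA category" carries number-at-risk rows by FDA class.
- "Figure 15.4.1 Logistic regression model" is labelled as discharge at Day 8 and takes Mild as the reference class. One of its rows reads "FDA Moderate vs Mild 0.0687 -2.6784 0.2528" (odds ratio, estimate, p-value). It also has rows for dose, age and baseline viral load.

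The introduction to Appendix V defines a good outcome by discharge before day 9.

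**The concern.** If every patient in the reference class has the same outcome, the logistic likelihood has no maximum. Coefficients against that class run off to infinity, their standard errors grow faster than the estimates, and Wald p-values tend to 1. The FDA rows of Table 12.1.24 would then reflect where the iteration stopped.

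The second issue is Figure 15.4.1 itself. It prints ordinary-looking finite FDA estimates, and their pattern does not match the counts a few pages earlier. If the estimator, the data or the modelled event is not what the label says, the dose rows are affected too. The 2.5 mg against 1.5 mg odds ratio of 0.0233 could mean a 43-fold fall or a 43-fold rise in the odds of discharge (1/0.0233 = 42.9). Dose selection is a study objective.

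**Working it through.** **Inputs** (at-risk rows under SAP Figure 15.1.2; 6 + 23 + 16 = 45, the planned total)

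| FDA class | N | At risk day 7 | Day 8 | Day 9 | Days 15 and 16 |
|---|---|---|---|---|---|
| Mild | 6 | 6 | 0 | 0 | 0 |
| Moderate | 23 | 23 | 4 | 1 | 0 |
| Severe | 16 | 15 | 8 | 7 | 1 |

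Assumption: leaving the risk set means discharge. The Day-8 cut has two readings:

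- **Cut A** (not discharged = at risk on day 8): 0/4/8, so discharged 6/6, 19/23, 8/16.
- **Cut B** (before day 9, as in Appendix V): 0/1/7, so discharged 6/6, 22/23, 9/16.

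**1. The printed rows.** exp(-2.6784) = 0.0687 and exp(-0.2517) = 0.7775, as printed. The implied Wald standard errors are 2.6784/1.144 = 2.34 and 0.2517/0.107 = 2.36. The rows agree with themselves.

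**2. Separation.** Mild is uniform under both cuts. All six leave in the same one-day step, so no whole-day cut divides them. Raising the fitted Mild logit alone always raises the likelihood, whatever covariates are added. Dropping patients with missing covariates does not help, because any subset with a Mild patient is still uniform in that class. Newton-Raphson under cut B:

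| Iterations | Moderate vs Mild | Severe vs Mild | SE |
|---|---|---|---|
| 8 | -6.1 | -9.0 | 41 |
| 16 | -14.1 | -17.0 | 2,221 |
| 25 | -23.1 | -26.0 | about 200,000 |

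Cut A behaves the same way. With invented dose, age and viral-load covariates, both FDA coefficients diverged in 200 of 200 fits.

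**3. What can still be estimated.** Severe against Moderate does not involve Mild. Odds ratios for discharge:

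- Cut A: (8/8)/(19/4) = 0.21; log -1.558, SE √(1/19 + 1/4 + 1/8 + 1/8) = 0.743, Wald p = 0.036.
- Cut B: (9/7)/(22/1) = 0.058; log -2.840, SE 1.140, Wald p = 0.013.

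**4. Joint 2-df tests.** As the Mild standard error grows, the joint Wald statistic tends to the squared Severe-against-Moderate z but is still referred to 2 df. For 2 df, p = exp(-statistic/2).

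| Test | Cut A | Cut B |
|---|---|---|
| Joint Wald | (1.558/0.743)² = 4.39, p = 0.111 | (2.840/1.140)² = 6.21, p = 0.045 |
| Likelihood ratio | 2(26.096 - 21.717) = 8.76, p = 0.0125 | 2(21.060 - 15.078) = 11.96, p = 0.0025 |
| Exact 3×2 | p = 0.022 | p = 0.0045 |

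**5. Firth estimates.** With FDA class alone, Firth's penalty amounts to adding ½ to each cell. Odds of discharge under cut A are 6.5/0.5 = 13, 19.5/4.5 = 4.33 and 8.5/8.5 = 1. The odds ratios against Mild are 0.33 (Moderate) and 0.077 (Severe). Under cut B they are 1.15 and 0.097. The penalised likelihood-ratio p for Severe against Mild is 0.03 (A) or 0.06 (B).

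**6. Figure 15.4.1 against the counts.** The implied Severe-against-Moderate odds ratio is 0.7775/0.0687 = 11.3, against a crude 0.21 or 0.06 for discharge.

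- If the event is discharge, both FDA coefficients should run to minus infinity, and Severe against Moderate points the wrong way.
- If the event is non-discharge, the crude Severe-against-Moderate odds ratio becomes 4.75 or 17.1, which suits 11.3. But Moderate against Mild should then run to plus infinity, and the figure prints -2.68.

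Neither event direction fits all the FDA rows.

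**7. Day 15.** Only one patient (Severe) remains at risk. Mild and Moderate are both fully discharged, so both are separated.

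**The case against.** The strongest reply is that the SAP does not specify the failing model in one place. Wald comes from a table shell and Mild as reference from a supportive figure. The shell names no estimator. The finite printed estimates may come from a penalised fit, other data, another coding or a stopped iteration. This stands as far as it goes: without patient data the cause cannot be diagnosed. It does not remove the need to state the method, because plain logistic regression is what a programmer would run from the text.

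Three stronger readings are tempting, and the documents do not support them:

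- *A reader might infer that the model cannot detect severity.* It can. Severe against Moderate has Wald p = 0.036 or 0.013, and the joint Wald test is only weakened. SAP 8.1 m) also plans Kaplan-Meier discharge curves by FDA class, which do not have this problem.
- *A reader might infer that severity would fail the 0.10 screen and leave dose unadjusted.* That needs a Wald screen and cut A. The SAP names no screening test. Where it does name one for categorical variables (Table 12.1.8) it is Fisher's exact test, and an exact test passes under both cuts. Figure 15.4.1 keeps FDA class alongside dose.
- *A reader might infer that separation corrupts the dose estimates.* Under maximum likelihood the separated Mild patients drop out, and the dose coefficients equal those from Moderate plus Severe. The dose rows are unreadable because the event direction is unclear.

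One further limit applies. The printed model is adjusted and the 0.21 and 0.06 are crude, so adjustment could account for some of the gap in the Severe-against-Moderate ratio. It cannot account for finite estimates against Mild.

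**Conclusion.** The point holds in limited form. On the SAP's own counts, ordinary maximum likelihood gives no finite odds ratio against Mild at Day 8, and Wald tests against Mild carry no information. The joint Wald p-value is about 9 times the likelihood-ratio one under cut A (0.111/0.0125) and 18 times under cut B (0.045/0.0025). The Day-15 model is worse. The finite FDA rows in Figure 15.4.1 are not ordinary maximum likelihood on the counts under Figure 15.1.2, and neither event direction reconciles the two displays. As printed, the dose odds ratios of 0.268 and 0.0233 have no readable direction.

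This rests on two assumptions: exits from the risk set are discharges, and the at-risk rows are study data and not a mock-up. Their total of 45 supports the second. If they are illustrative the SAP should say so; with so few Mild patients a rule for separation is still worth having. The SAP calls its analyses descriptive and the primary objective is safety, so this is a modest-priority correction to an exploratory model.

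**What to change.** In SAP 8.1 l), Tables 12.1.24 and 12.1.25 and Figure 15.4.1:

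1. Use Firth-penalised logistic regression with profile-likelihood confidence limits and penalised likelihood-ratio p-values. Use the same test for the p < 0.10 screen, and say so.
2. State the modelled event and the day cut in each title, for example discharged alive by Day 8, and make it agree with the Appendix V outcome definition.
3. Refit Figure 15.4.1, state its estimator and population, and reconcile it with Figure 15.1.2.
4. Print discharged/total beside each category. For Day 15 this matters most: penalisation will return finite numbers, but one undischarged patient cannot inform a multivariable model.

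The cost is one model option, a sentence or two in the SAP and a refit. Penalised estimates are slightly shrunk, a small price here. Merging Mild into Moderate is not recommended, because it would be a category choice made after seeing the outcomes.
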